8.1 TRIAL APPROVAL, PATIENT INFORMATION, INFORMED CONSENT

This trial will be initiated only after all required legal documentation has been reviewed and approved by the respective Institutional Review Board (IRB) / Independent Ethics Committee (IEC) and competent authority (CA) according to national and international regulations. The same applies for the implementation of changes introduced by amendments.

Prior to patient participation in the trial, written informed consent must be obtained from each patient (or the patient's legally accepted representative) according to ICH / GCP and to the regulatory and legal requirements of the participating country. Each signature must be personally dated by each signatory and the informed consent and any additional patient-

information form retained by the investigator as part of the trial records. A signed copy of the informed consent and any additional patient information must be given to each patient or the patient's legally accepted representative."

The patient must be given sufficient time to consider participation in the trial. The investigator obtains written consent of the patient's own free will with the informed consent form after confirming that the patient understands the contents. The investigator (or delegate) must sign (or place a seal on) and date the informed consent form. If a trial collaborator has given a supplementary explanation, the trial collaborator also signs (or places a seal on) and dates the informed consent.

Re-consenting may become necessary when new relevant information becomes available and should be conducted according to the sponsor's instructions.

The consent and re-consenting process should be properly documented in the source documentation.

8.2 DATA QUALITY ASSURANCE

A quality assurance audit/inspection of this trial may be conducted by the sponsor, sponsor's designees, or by IRB / IEC or by regulatory authorities. The quality assurance auditor will have access to all medical records, the investigator's trial-related files and correspondence, and the informed consent documentation of this clinical trial.

8.3 RECORDS

CRFs for individual patients will be provided by the sponsor. See [section 4.1.5.2](#) for rules about emergency code breaks. For drug accountability, refer to [section 4.1.8](#).

8.3.1 Source documents

In accordance with regulatory requirements the investigator should prepare and maintain adequate and accurate source documents and trial records that include all observations and other data pertinent to the investigation on each trial patient. Source data as well as reported data should follow good documentation practices and be attributable, legible, contemporaneous, original and accurate. Changes to the data should be traceable (audit trail).

Data reported on the CRF must be consistent with the source data or the discrepancies must be explained.

The current medical history of the patient may not be sufficient to confirm eligibility for the trial and the investigator may need to request previous medical histories and evidence of any diagnostic tests. In this case the investigator must make three documented attempts to retrieve

previous medical records. If this fails a verbal history from the patient, documented in their medical records, would be acceptable.

During the site visit the sponsor's CRA or auditor must be granted access to the original patient file (please see [section 8.3.2](#)). The investigator must ensure that all patient identifiers (e.g. patient's name, initials, address, phone number, social security number) have properly been removed or redacted from any copy of the patients' source documents before sending them to the sponsor.

If the patient is not compliant with the protocol, any corrective action e.g. re-training must be documented in the patient file.

For the CRF, data must be derived from source documents which must be stored appropriately, for example:

- Patient identification: gender, year of birth (in accordance with local laws and regulations)
- Patient participation in the trial (substance, trial number, patient number, date patient was informed)
- Dates of patient's visits, including dispensing of trial medication
- Medical history (including trial indication and concomitant diseases, if applicable)
- Medication history
- Adverse events (onset date (mandatory) and end date (if available))
- Serious adverse events (onset date (mandatory), and end date (if available))
- Concomitant therapy (start date, changes)
- Originals or copies of laboratory results, images and report of echocardiogram (from Visit 1) for the assessment of LVEF, ECG tracings and other imaging or testing results, with proper documented medical evaluation (in validated electronic format, if available)
- Completion of patient's participation in the trial" (end date; in case of premature discontinuation document the reason for it).
- Prior to allocation of a patient to a treatment into a clinical trial, there must be documented evidence in the source data (e.g. medical records) that the trial participant meets all inclusion criteria and does not meet any exclusion criteria. The absence of records (either medical records, verbal documented feedback of the patient or testing conducted specific for a protocol) to support inclusion/exclusion criteria does not make the patient eligible for the clinical trial.

8.3.2 Direct access to source data and documents

The sponsor will monitor the conduct of the trial by regular on-site monitoring visits and in-house data quality review. The frequency of site monitoring will be determined by assessing all characteristics of the trial, including its nature, objective, methodology and the degree of any deviations of the intervention from normal clinical practice.

The investigator /institution will allow site trial-related monitoring, audits, IRB / IEC review and regulatory inspections. Direct access must be provided to the CRF and all source documents/data, including progress notes, copies of laboratory and medical test results, which

must be available at all times for review by the CRA, auditor and regulatory inspector (e.g. FDA). They may review all CRFs and informed consents. The accuracy of the data will be verified by direct comparison with the source documents described in [section 8.3.1](#). The sponsor will also monitor compliance with the protocol and GCP.

8.3.3 Storage period of records

Trial site(s):

The trial site(s) must retain the source and essential documents (including ISF) according to contract or the local requirements valid at the time of the end of the trial (whatever is longer).

Sponsor:

The sponsor must retain the essential documents according to the sponsor's SOPs.

8.4 EXPEDITED REPORTING OF ADVERSE EVENTS

BI is responsible to fulfil their legal and regulatory reporting obligation in accordance with regulatory requirements.

8.5 STATEMENT OF CONFIDENTIALITY AND PATIENT PRIVACY

Individual patient data obtained as a result of this trial is considered confidential and disclosure to third parties is prohibited with the exceptions noted below. Patient privacy will be ensured by using patient identification code numbers.

Data protection and data security measures are implemented for the collection, storage and processing of patient data in accordance with the principles 6 and 12 of the World Health Organization (WHO) GCP handbook.

Treatment data may be given to the patient's personal physician or to other appropriate medical personnel responsible for the patient's welfare. Data generated as a result of the trial need to be available for inspection on request by the participating physicians, the sponsor's representatives, by the IRB / IEC and the regulatory authorities.

8.6 TRIAL MILESTONES

The **start of the trial** is defined as the date when the first patient in the whole trial signs informed consent.

The **end of the trial** is defined as the date of the last visit of the last patient in the whole trial ("Last Patient Out").

The **"Last Patient Drug Discontinuation"** (LPDD) date is defined as the date on which the last patient at an individual trial site ends trial medication (as scheduled per protocol or

prematurely). Individual investigators will be notified of SUSARs occurring with the trial medication until 30 days after LPDD at their site.

Early termination of the trial is defined as the premature termination of the trial due to any reason before the end of the trial as specified in this protocol.

Temporary halt of the trial is defined as any unplanned interruption of the trial by the sponsor with the intention to resume it.

Suspension of the trial is defined as an interruption of the trial based on a Health Authority (HA) request.

The IEC / competent authority in each participating EU member state will be notified about the trial milestones according to the respective laws.

A final report of the clinical trial data will be written only after all patients have completed the trial in all countries (EU or non-EU) to incorporate and consider all data in the report. The sponsor will submit to the EU database a summary of the final trial results within one year from the end of a clinical trial as a whole, regardless of the country of the last patient (EU or non-EU).

8.7 ADMINISTRATIVE STRUCTURE OF THE TRIAL

The trial is sponsored by Boehringer Ingelheim (BI).

Two Coordinating Investigators are responsible to coordinate investigators at the different sites participating in this trial. Tasks and responsibilities are defined in a contract.

An Executive Committee (ExC) consisting of independent experts (the Coordinating Investigators of this trial and of the 1245-0168 trial) and sponsor representatives will be established to support the Sponsor in designing the trials and successful execution. The composition of the ExC will be documented in the Trial Master File (TMF). The tasks and responsibilities will be agreed in contracts between the ExC members and the sponsor.

A Steering Committee (SC) consisting of independent experts and sponsor representatives will be established to support the Coordinating Investigators who will be the chairs of the SC. The composition of the SC will be documented in the Trial Master File (TMF). The tasks and responsibilities will be agreed in contracts between the SC members and the sponsor.

A Data Monitoring Committee (DMC) will be established. Members of the DMC are independent of BI, they are physicians experienced in the treatment of the disease under investigation and a statistician. The DMC will evaluate safety data. While DMC members may be unblinded, measures are in place to ensure the blinding for everyone else involved in the trial. Regular DMC meetings will be held at specified intervals. The DMC will recommend continuation, modification or termination of the trial as detailed in the DMC charter. DMC recommendations as well as the final BI decision will be reported to the

appropriate Regulatory Authorities (RAs)/ HAs, IRBs/ECs, and to investigators as requested by local law. The tasks and responsibilities of the DMC are specified in a charter.

An independent external committee (Clinical Event Committee, [CEC]) will be established to adjudicate certain hepatic events and ketoacidosis.

Hepatic External adjudication for hepatic events

Certain hepatic events will be adjudicated by external independent experts for severity and causal relationship with the trial medication; both in a blinded fashion. Events to be reviewed will be defined in a hepatic charter.

Events may either be defined by abnormal laboratory values and/or relevant adverse events or both.

For qualifying events, relevant source documents generated from any medical evaluations of these events will be requested including for example laboratory values, histological analysis, reports from ultrasound, computed tomography (CT), magnetic resonance imaging (MRI), scintigraphy, hospital discharge letters, and medical reports from other physicians. All evaluations will be performed in a blinded fashion. The assessments will be analysed based on empagliflozin data combined from multiple trials (i.e. on project level).

Adjudication of ketoacidosis

Events suspected to be metabolic acidosis, ketoacidosis and DKA will be adjudicated by independent external experts in a blinded fashion.

Relevant documentation on the participating (Principal) Investigators (e.g. their curricula vitae) will be filed in the ISF. The investigators will have access to the BI clinical trial portal (Clinergize) to facilitate document exchange and maintain electronic ISF.

BI has appointed a Trial Clinical Monitor (TCM), responsible for coordinating all required activities, in order to

- manage the trial in accordance with applicable regulations and internal SOPs,
- direct the clinical trial team in the preparation, conduct, and reporting of the trial,
- ensure appropriate training and information of CMLs, CRAs, and investigators of participating countries.

The organisation of the trial in the participating countries will be performed by the respective local or regional BI-organisation (Operative Unit, [OPU]) in accordance with applicable regulations and BI SOPs, or by a CRO with which the responsibilities and tasks will have been agreed and a written contract filed before initiation of the clinical trial.

Data Management and Statistical Evaluation will be done by BI according to BI SOPs.

Tasks and functions assigned in order to organise, manage, and evaluate the trial are defined according to BI SOPs. A list of responsible persons and relevant local information can be found in the ISF.

A central laboratory service and an IRT vendor will be used in this trial. Details will be provided in the IRT Manual and Central Laboratory Manual, available in the ISF.

10. APPENDICES

10.1 SIX MINUTE WALK TEST

10.1.1 General considerations for exercise testing

The methodology of the six minute walk test protocol is based on recommendations outlined by the American Thoracic Society (2002) [[R03-0725](#), [R17-3628](#)].

10.1.2 Exercise performance variability

A number of physiological and psychological factors are known to affect exercise performance. Lack of attention to controlling these extraneous factors may result in a certain degree of variability in exercise performance. As such, the following pre-defined requirements have been put in place to reduce exercise performance variability:

Physiological:

- The patient's usual medical regimen should be continued
- Pre-exercise diet: Subjects are to be encouraged to eat breakfast before coming to the clinic. However, subjects should not eat within 2 hours of exercise tests.
- Hydration state: Subjects are to be encouraged to maintain an adequate hydration state during the morning of the exercise tests.
- Environmental conditions (temperature, humidity): Temperature and humidity should be controlled within the testing environment at comfortable levels.

Previous exercise:

- Fatigue: Subjects should be encouraged to stay well-rested and to refrain from any strenuous, fatiguing or exhausting activities (e.g., walking up hills, walking up many flights of stairs, running, cycling, shovelling snow, strenuous household chores) on the morning of exercise tests.
- Delayed onset muscular soreness (DOMS): Very strenuous, heavy type of activities, especially activities to which the subject is unaccustomed, can lead to muscle soreness 24-48 hours after the activity. Subjects should be encouraged to refrain from any type of heavy lifting, exhaustive digging in the garden etc., for 2-3 days prior to each clinic visit, especially if the subject has not performed these activities recently.

Psychological:

- Verbal encouragement: During exercise testing, the wording and intensity of verbal encouragement provided to the subject will be standardized, and will preferably only be

provided by one member of the trial team. Appropriate positive words should be used to encourage the patient to continue walking.

- Familiarity with surroundings: Trial staff should allow as much time as necessary for the subject to become comfortable with the testing environment surroundings.
- Distractions: During the exercise tests, access to the testing environment should be restricted to trial staff as much as possible. The noise level in the testing environment should be kept to a minimum, except for those sounds specifically related to the conduct of the test. This will ensure that the subject is able to concentrate on the task at hand, and will also ensure that the subject is attentive to the verbal encouragement provided by the designated member of the trial team.
- Comfort during the test: Subjects should be appropriately dressed for exercise (e.g., shorts or track pants, gym shoes, T-shirt or sweat shirt), and should use their usual walking aids during the test (cane, walker, etc.). Trial staff should ensure that the subject is comfortable with the environment prior to starting the exercise.
- Familiarity with test: Before starting exercise, a member of the trial team should make sure that the subject is completely familiar with the type of exercise that is to be performed.
- Performance incentives: No external incentives for performance (i.e., rewards for performance) should be given to the subject, especially as the subject nears the point of limitation, but also prior to or at any time during the exercise.

Heart rate and safety monitoring

- Heart rate and blood pressure will be measured before exercise, at end-exercise, five minutes after termination of exercise and when, for clinical reasons, it is required.

Personnel qualifications

- Exercise challenges should be conducted by adequately trained personnel with a basic knowledge of exercise physiology.
- Technicians familiar with normal and abnormal responses during exercise and trained in cardiopulmonary resuscitation (CPR) should be present throughout the test (see Safety Issues).
- Medically qualified personnel are required to be present for the first test. However, the supervising physician must be readily available during all tests to respond as needed. The degree of subject supervision should be increased if warranted by the clinical status of the subject.

10.1.3 Safety issues

Relative Contraindications:

The following conditions that preclude exercise testing should be assessed at each site visit prior to the 6MWT and patients with any of these findings can return to the study site within the visit window to complete the 6MWT if these measurements are resolved:

- Acute decompensated heart failure,
- A resting heart rate > 120bpm, SBP > 180mmHg and diastolic blood pressure (DBP) > 100mmHg.
- Symptomatic hypotension and symptomatic bradycardia
- Any condition that, in the opinion of the investigator, would impact the ability of the patient to perform the 6MWT

Stable exertional angina is not an absolute contraindication for a 6MWT, but patients with these symptoms should perform the test after using their antiangina medication, and rescue nitrate medication should be readily available.

Stopping rules:

Cardiac (e.g. bradyarrhythmias, ventricular tachycardia, myocardial infarction, heart failure, hypotension, and shock) and non-cardiac (musculoskeletal trauma, severe fatigue, dizziness, fainting, body aches) complications of exercise challenges have been reported.

Consequently during the test, study personnel should be alert to any abnormal event.

Indications to stop the test must be clearly established and known by the personnel involved in testing. Such symptoms are listed below:

- Acute chest pain,
- Sudden pallor,
- Loss of co-ordination / staggering,
- Mental confusion,
- Extreme dyspnea,
- Leg cramps,
- Diaphoresis.

The subject will be withdrawn from performing the 6MWT should any of these symptoms occur.

Safety requirements and rescue medication:

If the exercise test has been stopped for one of these reasons, the subject should be monitored in the laboratory until signs / symptoms / ECG modifications have completely cleared.

Adequate safety equipment must be available at the test site according to local institutional

requirements and emergency medications are to be administered at the discretion of the Investigator such as:

- Oxygen,
- Fast-acting nitrate
- Antiplatelet agent
- Sphygmomanometer
- Telephone
- Automated electronic defibrillator or other safety measures as per institutional requirements

10.1.4 Conduct of the 6MWT

Location of the 6MWT:

The 6MWT should be performed indoors, along a long, flat, straight, enclosed corridor with a hard surface that is seldom traveled. The walking course must be 30 m in length and therefore a 100-ft hallway is required. The length of the corridor should be marked every 1m to 3m however the recommendation is to mark the course every 1m. The turnaround points should be marked with a cone (such as an orange traffic cone) and placed 0.5m from each extremity to enable the subject to not have to turn too abruptly. A starting line, which marks the beginning and end of each 60-m lap, should be marked on the floor using brightly colored tape.

Required equipment for the 6MWT:

The following equipment is required by the staff:

- Countdown timer
- Mechanical lap counter
- Two cones to mark the turnaround points
- A chair that can be easily moved along the walking course
- Worksheet on a clipboard
- Borg CR-10 scale
- 30 meters measuring tape
- Safety requirements as outlined in [Section 10.1.3](#)

Measurements:

- Repeat testing should be performed about the same time of day to minimize intraday variability.
- A “warm-up” period before the test should not be performed.

- The patient should sit at rest in a chair, located near the starting position, for at least 5 minutes before the test starts. During this time, check for contraindications, measure heart rate and blood pressure, and make sure that clothing and shoes are appropriate.
- Set the lap counter to zero and the timer to 6 minutes. Assemble all necessary equipment (e.g. lap counter, timer, worksheet, BORG CR-10 scale) and move the patient to the starting point.
- The patient should be asked to rate their baseline breathing discomfort and overall fatigue using the Borg Scale.
- The patient should be instructed as follows:
 - “The object of this test is to walk as far as possible for 6 minutes. You will walk back and forth in this hallway. Six minutes is a long time to walk, so you will be exerting yourself. You will probably get out of breath or become exhausted. You are permitted to slow down, to stop, and to rest as necessary. You may lean against the wall while resting, but resume walking as soon as you are able.
 - You will be walking back and forth around the cones. You should pivot briskly around the cones and continue back the other way without hesitation. Now I’m going to show you. Please watch the way I turn without hesitation.”
 - Demonstrate by walking one lap yourself. Walk and pivot around a cone briskly.
 - “Are you ready to do that? I am going to use this counter to keep track of the number of shuttles (distance between the two cones) you complete. I will click it each time you turn around at this starting line. Remember that the objective is to walk AS FAR AS POSSIBLE for 6 minutes, but don’t run or jog.
 - Do you have any questions? Are you ready to start? Start now.”
- You should stand near the starting line during the test. Do not walk with the patient. As soon as the patient starts to walk, start the timer.
- Do not talk to anyone during the walk. Use an even tone of voice when using the standard phrases of encouragement. Watch the patient. Do not get distracted and lose count of the shuttles. Each time the patient walks one length of the corridor, click the lap counter once (and mark the shuttle on the worksheet). Let the participant see you do it.
 - After the first minute, tell the patient the following (in even tones): “You are doing well. You have 5 minutes to go.”
 - When the timer shows 4 minutes remaining, tell the patient the following: “Keep up the good work. You have 4 minutes to go.”

- When the timer shows 3 minutes remaining, tell the patient the following: “You are doing well. You are halfway done.”
- When the timer shows 2 minutes remaining, tell the patient the following: “Keep up the good work. You have only 2 minutes left.”
- When the timer shows only 1 minute remaining, tell the patient: “You are doing well. You have only 1 minute to go.”
- Do not use other words of encouragement (or body language to speed up).
- If the patient stops walking during the test and needs a rest, say this: “You can lean against the wall if you would like; then continue walking whenever you feel able.” Do not stop the timer. While the patient is stopped, standardised encouragement should be provided every 30 seconds: “Please resume walking whenever you feel able.” The time that the patient stopped and the time that walking is recommenced should be recorded.
- If the patient stops before the 6 minutes are up and refuses to continue (or you decide that they should not continue), wheel the chair over for the patient to sit on, discontinue the walk, and note on the worksheet the distance, the time stopped, and the reason for stopping prematurely.
- When the timer is 15 seconds from completion, say this: “In a moment I’m going to tell you to stop. When I do, just stop right where you are and I will come to you.”
- When the timer rings (or buzzes), say this: “Stop!” Walk over to the patient. Consider taking the chair if they look exhausted. Mark the spot where they stopped by placing a bean bag or a piece of tape on the floor.
- At the end of exercise the blood pressure and heart rate should be recorded. Repeat blood pressure and heart rate measurements will be taken 5 minutes later to assess recovery rate.
- The patient should be asked to rate their end of exercise breathing discomfort and overall fatigue using the Borg Scale.
- Record the number of shuttles from the counter (or tick marks on the worksheet).
- Record the additional distance covered (the number of meters in the final partial shuttle) using the course distance markers. Calculate the total distance walked, rounding to the nearest meter, and record it on the worksheet.
- Congratulate the patient on good effort and ask if they have any symptoms.

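### Appendix 10.1.4 gives two click rules for the 6MWT counter: one patient-script sentence counts laps, while the staff instruction counts corridor lengths

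*Protocol*

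**What the plan says.** Protocol Appendix 10.1.4 sets out the course, the script and the recording steps.

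- **Course.** "The walking course must be 30 m in length and therefore a 100-ft hallway is required". On the cones: "The turnaround points should be marked with a cone (such as an orange traffic cone) and placed 0.5m from each extremity". The floor marking is described as "A starting line, which marks the beginning and end of each 60-m lap".
- **Script to the patient.** "I am going to use this counter to keep track of the number of shuttles (distance between the two cones) you complete", followed at once by "I will click it each time you turn around at this starting line".
- **Instruction to the tester, a few lines later.** "Each time the patient walks one length of the corridor, click the lap counter once", with a mark on the worksheet for each shuttle.
- **Recording.** The tester enters the number of shuttles, taken from the counter or from the worksheet marks. The next step is "Record the additional distance covered (the number of meters in the final partial shuttle) using the course distance markers", and then a total to the nearest metre. No step gives the metres in one full shuttle.

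This is current text. Global Amendment 1 edited the script sentence that follows the clicking sentence and left the clicking sentence as it was.

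Protocol 5.1.1 makes a patient a screen failure if any screening or Visit 2 test exceeds 350 m, or if the largest Visit 2 distance is below 100 m. It also says that the method is described in the investigator site file.

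**The concern.** The two click rules differ by a factor of two, and the script's rule is easy to pick up. The device is called a lap counter, a lap is 60 m, and the tester stands near the starting line, where the script says the click happens. The count is then entered as shuttles, which are single lengths.

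The recorded distance decides eligibility at both limits and gives the primary endpoint. The trial is sized on a difference of 30 m (Protocol 7.7), so a halved result at one visit would put an error several times that size into a patient's change from baseline.

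The SAP's check on test conduct (Table 6.2: 1, code G3.48) compares conduct with the protocol, and the protocol carries both rules.

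**Working it through.** The plan gives no worked distance to reproduce, so the check sets the instructions side by side and follows each one through to the recorded result.

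**1. Clicks per lap.** There is one starting line, and a patient turns at it once per 60 m.

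- Script sentence: 1 click per 60 m.
- Tester instruction: 2 clicks per 60 m.
- Ratio: 2.

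**2. Which rule is out of line.**

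| Element of Appendix 10.1.4 | Unit counted |
|---|---|
| Script: what the counter tracks | shuttle, cone to cone |
| Script: when the click happens | turn at the starting line, so one lap |
| Tester instruction | one corridor length |
| Worksheet mark | shuttle |
| Recording step | shuttle |

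Four elements agree on one click per length. Only the clicking sentence of the script differs, and it contradicts the sentence just before it.

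**3. Effect if the script's clicks are recorded as shuttles.** Assume that each click is credited at 30 m and that the worksheet marks are not used. For a true distance d:

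recorded = 30 × floor(d/60) + leftover metres

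The leftover can be read as the metres in the final partial length (d mod 30) or as the metres since the last click (d mod 60).

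| True d (m) | Clicks | Recorded, d mod 30 | Recorded, d mod 60 |
|---|---|---|---|
| 100 | 1 | 30 + 10 = 40 | 30 + 40 = 70 |
| 250 | 4 | 120 + 10 = 130 | 120 + 10 = 130 |
| 300 | 5 | 150 + 0 = 150 | 150 + 0 = 150 |
| 350 | 5 | 150 + 20 = 170 | 150 + 50 = 200 |
| 400 | 6 | 180 + 10 = 190 | 180 + 40 = 220 |

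Under either reading a 400 m walk is recorded below the upper limit, and a 100 m walk falls under the lower one. The exact distances at which a patient changes side depend on the leftover rule, so none are stated here.

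**4. Effect on change from baseline.**

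- A patient walks 300 m at both visits, counted by length at baseline and by the script at week 12. The recorded change is 150 − 300 = −150 m; the true change is 0.
- A patient walks 240 m and then 300 m, both counted by the script. The records are 4 × 30 = 120 and 5 × 30 = 150, a change of +30 m; the true change is +60 m.

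**5. Metres per length.**

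- From the lap: 60/2 = 30 m.
- From the cones, if the extremity is the end of the 30 m course: 30 − 2 × 0.5 = 29 m.
- From the cones, if the extremity is the end of the 100-ft hallway: 30.48 − 1 = 29.48 m.

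Crediting 29 m in place of 30 m removes 1 m per completed length (1/30 = 3.3%). A record of 350 m becomes 11 × 29 + 20 = 339 m, and 100 m becomes 3 × 29 + 10 = 97 m. Applied uniformly, the planned 30 m difference becomes 29 m and the SD of 72 m becomes 72 × 29/30 = 69.6 m. Since 29/69.6 = 30/72 = 0.417, sample size and power do not change.

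**The case against.** The strongest reply is that the faulty sentence is spoken to the patient, while the tester's own instruction is explicit. This stands. It is the reason to call the script sentence the error, and not to call the counting rule undefined.

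Halving also needs several failures together: clicking per lap, crediting 30 m per click, and leaving the worksheet marks unused. A tester who clicks per lap and credits 60 m gets the right answer (5 × 60 = 300 m). This stands too, and makes the consequence conditional.

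There are safeguards. Testers must be qualified, and the same staff are used where possible (Flow Chart footnote 7). Monitors check G3.48 at the site. At Visits 2 and 4 the longer of two tests is used, so one halved test would normally be overridden by a correct one, and the endpoint suffers only if both tests of a visit are counted wrongly. These points lower the risk but do not remove the contradiction. With about 80 sites and about 4 patients at each (Protocol 3.3), a tester has little routine in which to notice the mistake.

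A reader might infer that distances were halved at some sites, or that a known amount of power is lost. The documents support neither. They give no miscount rate, nothing shows that any tester followed the script sentence, and a power figure would need error rates and a baseline distribution that appear nowhere in the plan.

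A reader might also infer that 29 m is the correct credit. That depends on what the extremity refers to, and patients walk around the cones. With an assumed turning radius of 0.5 m, the path per length is 29 + 0.5π, about 30.6 m, which is nearer 30 than 29.

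**Conclusion.** The contradiction is real and sits in the working instructions for the primary measurement. The script sentence is wrong and should be corrected.

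The possible error is large for an affected test, about half the distance. It rests on three assumptions: the tester follows the script, credits 30 m per click, and does not use the worksheet marks. It would not favour either arm, because the wording is the same for all patients in a double-blind trial. Its frequency cannot be estimated from the documents, and the site file or worksheet may already give the right rule.

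The missing metres per length is a minor clarification. It is worth about 3%, has no effect on power if one figure is used throughout, and matters only for walks close to an entry limit.

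**What to change.** - Reword the script sentence so that the click comes each time the patient completes a length, that is, at a turn at either cone.
- Confirm that the investigator site file and the worksheet use the same rule.
- State one fixed crediting distance per length. The course length and the lap wording point to 30 m. Make the shuttle definition and the cone placement consistent with the stated figure.
- Write the total as completed lengths × that figure + metres in the final partial length.

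The cost is one script sentence, one stated figure, a check of two site documents and a short reminder to sites. No procedure is added, and the sample size is unchanged.
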